In addition to enrichment with family history, we will perform *APOE* genotyping on potential participants. Although the REVEAL Study has focused on the disclosure of *APOE*, in this research project we do not want to conflate disclosure of an AD risk gene variant with the disclosure of an AD biomarker, so the results of *APOE* genotyping will not be returned to the

participants. Instead, *APOE* genotyping will be used to increase the mix of participants who are $\epsilon 4+$ to at least 50%.

“We will not be sharing the results of subjects’ *APOE* genotyping because we, and each clinical study site, will be blinded to these results. *APOE* results will be only used to enrich our study sample to ensure we are effectively randomizing 50% elevated amyloid scans vs. not-elevated amyloid scans into each intervention arm. These *APOE* results will only be reported to the centralized data site, Boston University, but not the other clinical sites (Brigham and Women’s Hospital, University of Pennsylvania, University of Michigan, and Duke University.”

Recruitment

All four sites have extensive experience in recruiting participants for AD clinical trials, with access to research registries of cognitively normal older individuals willing to participate in AD-related studies. Participants will be recruited using a variety of methods including interactions with family members of patients in memory clinics; review of research registries; clinical trials websites; direct referral from neurologists, geriatricians and local Alzheimer’s Association chapters; and talks in the community. We will post information about this study on our website, and on social media. We will use trifold brochures in clinician offices and at appropriate forums. The study will be mentioned in grand rounds, local clinic presentations on AD, and media interviews.

No “cold calls” will be made directly to any potential participant, whether identified from a patient database or medical record, without the consent of the patient and the patient’s primary physician or specialist.

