Finally, the Everyday Discrimination Scale⁶² has been developed and will be used to assess perceived discrimination.

Step 6 – Phone call #3: Confirm eligibility/ineligibility + Schedule Scan

The study coordinator will call the participant within two weeks of Visit #2. If the participant is not screened out, he/she is eligible to continue with study participation. If eligible, the study coordinator will schedule the participant's PET scan at their site's imaging center, This visit should happen within approximately one month of Visit #2. A study coordinator will also call to schedule the disclosure session (Visit #4) within approximately two weeks from when the scan results are returned to Boston University.

Step 7 – Visit #3: Amyloid Neuroimaging Scan + Randomization

At this third in-person visit, participants who pass the above listed screening measures will undergo amyloid imaging via a scheduled PET scan at each site's respective imaging center. Participants will receive a single intravenous administration of approximately 370 MBq (10 mCi) of florbetapir F 18 amyloid imaging agent. Participants will be positioned in the PET scanner and at 50 ± minutes after injection.

Imaging data from this scan visit will be sent to Molecular NeuroImaging (MNI) electronically through a secure, already existing Web upload process. The imaging data will undergo a comprehensive quality control process consisting of both a technical and scientific quality control. MNI has already worked with, and received images from, all of the imaging centers in this study and has experience with all study site cameras. Imaging interpretations from MNI will be sent directly to our centralized data site, Boston University, labeled with study ID and de-identified personal health information.

Boston University will randomize the participants into either (1) Comparison/non-disclosure arm (D+): participants will learn the results of their amyloid scans at Visit #4 or (2) Intervention/disclosure arm (D-): participants will not learn their scan results at Visit #4, but will return for another in-person visit (Visit #7) after the completion of their 6-month follow-up (Visit #6) for a delayed disclosure visit. Participants are randomized with a 1:1 randomization for non-disclosure arm: disclosure arm. For participants who are randomized in the disclosure arm, their amyloid imaging results of "elevated" or "not elevated" amyloid will be returned to their respective sites.

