Molecular NeuroImaging (MNI) will ensure standardized acquisition of ^{18}F -amyvid (AV-45) PET data at each of the study sites. MNI has developed a comprehensive setup procedure to reduce variance in the imaging outcome among sites that has been used in numerous multicenter amyloid PET imaging studies. MNI has already worked with, and received images from, all of the imaging centers in this study and has experience with all study site cameras. MNI's setup includes review of the imaging protocol with site personnel, set-up of the imaging acquisition protocol on the site camera. Following MNI site approval, each site will acquire ^{18}F -amyvid (AV-45) PET imaging using the protocol currently in use in both ADNI and the A4 study. Imaging data will be sent to MNI electronically through an already existing secure Web upload process. The imaging data will contain the subjects' assigned study number, and will not contain personal identifiable information. The imaging site will send the subjects' PET image to MNI and undergo a comprehensive quality control (QC) process consisting of both a technical (documenting receipt, naming convention, assessing for camera artifacts, etc) and scientific quality control (review by an imaging expert to ensure adequate for analysis). Imaging sites will provide scan transfer data and ongoing camera log information with each scan. Sites will be queried if data does not meet the study standards. Typically data quality control processes are completed within 3-5 days to enable the scans to continue data analysis. MNI will return the scan

results to BU, and BU will randomize and return the results to each of the clinical sites such that 50% are in the initial amyloid scan disclosure group and 50% are in the delayed disclosure group at the end of the study.

To minimize the risk of disclosing amyloid PET results in the EPIC record, scan results will be classified as a “PET research exam entry” that discloses that a research study was conducted and will not include the study name or any interpretable images for incidental findings. Scan orders and results will only be viewable by designated research staff (i.e., study coordinator, site PI and PET imaging center staff).

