Eyetracking data and questionnaire data from the 6-month follow-up visit related to stereotype threat and the digit span task will be analyzed by the University of Southern California (USC) team. All data will be de-identified before being sent to USC for analysis. Each site will upload their de-identified, raw pupillometry data (labeled with subject ID#) to the BU secure Web data repository and from there it will be sent to USC.

Data Analysis

The analytical strategy will focus on comparing A+D+ and A+D- groups on the ADCS-PACC score at 6 months to better identify if non-disclosure itself had an effect on ADCS-PACC performance. Although the primary comparison is not based on the fully randomized groups, it is a comparison of randomized groups in the pre-specified subgroup of A+ subjects, thus controlling for type 1 error. The power calculation is based on the comparison within the subgroup of A+ subjects, so type 2 error is also controlled. Our primary analysis will use a mixed-effects model repeated measures (MMRM)⁵⁷ approach to evaluate the three repeated measures over time. This Intention-to-Treat (ITT) analysis will incorporate information from those who drop out over the 6 months, assuming missing at random, and have better control of type 1 error and power. We will model time as a categorical measure, and the primary outcome will be the estimated difference (contrast) between the two groups at 6 months. As randomization may not be fully successful in balancing confounding factors between the groups (subgroups of the randomized groups), the analysis will also adjust for potentially confounding measures such as sex, age and *APOE* genotype. We will also include the baseline measure of the ADCS-PACC score in one regression model (using the two repeated measures at 6 weeks and 6 months) to allow for differences in cognitive functioning at baseline. We will also consider models that examine change from baseline, with and without adjustment for the baseline measure.

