Based on this calculation, we have set a target to enroll n=50 in each of the 2 elevated amyloid groups (A+D-, A+D+). Due to a much lower than anticipated rate of amyloid positivity and a dropout rate of approximately 10%, we plan to enroll 370 total participants and achieve 100 completed 6 month visits to reach our group enrollment targets of n=50 for each elevated amyloid group.

VII. Risks and Discomforts

Psychological risks: We recognize that persons with normal cognition who learn they have elevated amyloid and an increased risk of developing AD dementia could experience psychological distress. We will monitor psychological well-being in our participants by pre-screening potential participants for anxiety and depression and administering standardized rating scales with pre-specified cut-off scores for affect and anxiety at scheduled follow-up visits after disclosure of PET amyloid imaging results. Additional monitoring and appropriate actions will be taken based on conversations between the study staff (clinician judgment) and participant.

For the 6-month visit digit-span task, we will examine how memory performance is affected by task instructions. Although the purpose of all the included cognitive measures is to assess the link between amyloid status and performance, during this task we will explicitly state this

relationship. Although we expect this to increase concerns about task performance, we do not expect this to create emotional distress. However, we will monitor responses. This will be done via conversations between the study staff (clinician judgment) and participant.

Deception: Mild deception will be used during the 6-month visit digit-span task. More specifically, during the initial trials of this task participants will be told that the purpose is to calibrate the equipment. No calibration will be conducted, but this instruction will reduce any evaluative concerns that may be felt by the participants. We do not anticipate this mild deception to create any distress. However, participants will be fully debriefed about this at the end of the study and their questions will be answered.

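### No stratification of the randomisation by amyloid status is described, although the primary comparison and its 50-per-arm target lie wholly within the amyloid-elevated subgroup

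*Protocol*

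**What the plan says.** **Allocation.** Protocol Section V, Step 7 gives the ratio: "Participants are randomized with a 1:1 randomization for non-disclosure arm: disclosure arm". Section VI, Data Coordination, adds the overall balance: "BU will randomize and return the results to each of the clinical sites such that 50% are in the initial amyloid scan disclosure group", with the other half in the delayed group. Neither the protocol nor the SAP mentions a stratification factor, blocking or minimisation.

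**Order of events.** Step 7 says "Imaging interpretations from MNI will be sent directly to our centralized data site, Boston University". Data Coordination then has the imaging laboratory return the "results to BU, and BU will randomize and return the results to each of the clinical sites". The centre therefore knows amyloid status when it allocates.

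**Primary comparison and target.** Section VI, Data Analysis, compares A+D+ with A+D- and notes that "it is a comparison of randomized groups in the pre-specified subgroup of A+ subjects". SAP Primary Analysis 1.1 is also confined to A+. Under Power Calculation, "we have set a target to enroll n=50 in each of the 2 elevated amyloid groups", to be reached as 100 completed 6-month visits.

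**Mix of scan results by arm.** The only mechanism mentioned is in Section III, where APOE results are used "to ensure we are effectively randomizing 50% elevated amyloid scans vs. not-elevated amyloid scans into each intervention arm".

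**Imbalance.** Data Analysis anticipates it ("As randomization may not be fully successful in balancing confounding factors between the groups (subgroups of the randomized groups") and answers with adjustment for measures such as sex, age and APOE genotype. The SAP adjusts for baseline PACC, visit timing and a Covid-19 indicator, and then for other confounders that differ between the arms at p<0.05.

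**The concern.** A 1:1 rule over everyone scanned controls the total in each arm. It does not control how the A+ participants, roughly 30% of the sample, divide between the arms. The power statement and the enrolment target are both written as 50 and 50 within A+, so the described rule leaves the planned quantity to chance.

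APOE enrichment does not fill the gap. Genotype acts on eligibility, before the scan. It changes the number of A+ participants who reach randomisation and has no influence on the arm each one is given.

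The omission is easy to avoid, because the natural stratifier is already in the hands of the centre that allocates. At stake are the A+ arm sizes and, to a small extent, power. Bias is not at stake.

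**Working it through.** **Inputs.** SD 2.2, difference 1.25, 50 per group, 80% power, 370 enrolled, about 10% dropout and 100 A+ completers (Protocol, Power Calculation); A+ about 30% (Protocol, Specific Aims); two-sided test, alpha 0.05 (SAP, Primary Analysis 1.1).

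**1. Reproduce the plan's figures.**
- Two-sample t-test, noncentrality = 1.25 / (2.2 × √(1/50 + 1/50)) = 1.25 / 0.44 = 2.84 on 98 degrees of freedom. Power is 80.3%, against the stated 80%.
- The smallest difference detectable with 80% power at 50 per arm is 1.245, matching the SAP's 1.2451.
- A+ completers: 370 × 0.30 × 0.90 = 99.9, matching the target of 100.

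**2. How unequal can the A+ arms be?** Take 100 A+ completers. The documents do not say which of two unstratified schemes would apply, so both are shown.

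| Scheme | Distribution of one A+ arm | 95% range | P(smaller arm <45) | P(smaller arm <40) |
|---|---|---|---|---|
| Overall 185/185 forced | Hypergeometric(370, 185, 100), SD 4.3 | 42-58 | 20% | 1.4% |
| Simple 1:1 | Binomial(100, 0.5), SD 5.0 | 40-60 | 27% | 3.5% |

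**3. What does that cost in power?** The same t-test with noncentrality 1.25 / (2.2 × √(1/n₁ + 1/n₂)):
- 50/50: 80.3%
- 45/55: 79.9%
- 42/58: 79.3%
- 40/60: 78.7%

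Averaged over the distributions in step 2, power is 80.0% (overall split forced) or 79.9% (simple 1:1). The average loss is about 0.3-0.4 points.

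**4. What does stratification buy once dropout is counted?** Take 370 × 0.30 = 111 A+ enrolled, with each participant dropping out independently with probability 0.10 (assumption). Completers in an arm of size a are then Binomial(a, 0.90).

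| Allocation within A+ | P(smaller completer arm <45) | P(smaller completer arm <50) |
|---|---|---|
| Blocked, 55/56 | about 3% | about 65% |
| Overall 185/185 forced | about 23% | about 84% |
| Simple 1:1 | about 30% | about 87% |

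Blocking removes most of the risk of a markedly small arm. It does not make 50 completers in each arm likely.

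**5. Covariates within A+.** For a binary covariate with 50% prevalence (assumed) and 50 per arm, the SD of the chance difference in proportions is √(0.5 × 0.5 × 2/50) = 0.10. A difference must reach about 1.96 × 0.10, or 20 percentage points, before a p<0.05 screen selects it. Smaller chance differences would go unadjusted under the SAP's rule.

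**The case against.** **The documents are silent.** They do not say that allocation ignores amyloid status. A reader might infer that the trial was in fact unstratified, but the text does not support that. A list stratified by scan result would fit everything written, including the aim in Section III and the 50-per-arm target. What stands is that no such stratification is described.

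**The comparison is sound without it.** A reader might also infer that restricting the primary analysis to A+ breaks the randomisation or inflates type 1 error. It does not. The scan precedes allocation, so A+D+ and A+D- are randomised groups, as the protocol itself argues. Chance imbalance is also partly handled by adjustment. This objection stands in full, and with the small power loss it limits the weight of the point.

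**Stratifying by amyloid does less than it may seem to.** It is tempting to say that it would secure 50 per arm. The target counts completed visits and dropout comes after allocation, so it cannot. It is also tempting to say that it would protect the African American A+ subgroup. It would not: amyloid strata leave the division of that subgroup between arms to chance, and the SAP already says the study is not powered for it. Race and APOE are likewise left unbalanced by design.

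**Prevalence matters more.** At the lower end of the 25-30% that the SAP reports, 370 × 0.25 × 0.90 = 83 A+ completers, and power is 72.5% even with equal arms. This is true, but it does not argue against a nearly free improvement.

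**It may be too late.** The protocol is dated November 2019 and the SAP April 2021, and the SAP describes the pandemic as affecting the end of the study. A changed list can help only those not yet allocated. This stands and shapes the fix.

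**Conclusion.** The point holds as a gap in the described allocation with a modest consequence. The documents give a 1:1 ratio and an overall even split, with no stratification by a variable that the allocating centre already holds and on which the primary analysis depends. APOE enrichment cannot do that work.

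The effect on power is under 2 points for any split as even as 40/60, and there is no bias. The real exposure is the arm-size target: a 20% to 27% chance, with 100 A+ completers, that the smaller arm is below 45. Which end applies depends on whether the overall 185/185 split is enforced, which the documents leave open. The reduction to about 3% under blocking (from about 23-30% on the same basis) assumes 111 A+ enrolled, an even split at entry and independent 10% dropout.

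**What to change.** 1. In Protocol Section V, Step 7 and Section VI, Data Coordination, state that the coordinating centre randomises 1:1 in permuted blocks within amyloid result (elevated / not elevated), and within site if block sizes allow. With four sites, the A+ strata would average about 111 / 4 ≈ 28 participants, so blocks would have to be short.
2. If site is a stratum, include it in the primary model. Amyloid status needs no term there, because it is constant within A+.
3. Replace the SAP's p<0.05 screen for the non-pandemic confounders with a fixed, pre-specified covariate set, such as the sex, age and APOE genotype already named in the protocol, keeping baseline PACC. Race and APOE balance belong here, since amyloid strata do not supply it.
4. For participants already allocated, document the method actually used, including any stratification or blocking, and rely on the fixed covariates.

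**Cost.** A change to the central allocation list and a sentence or two in each document. The list change helps only participants not yet allocated. Allocation is central and Step 7 returns results to sites for the disclosure arm only, so stratifying need not reveal any D- result to a site.
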